5.8.2. Early IgAN Interim Analysis

If appropriate, an early interim analysis may be conducted for the IgAN disease cohort at the discretion of Alexion for the purpose of facilitating Phase 3 study planning and will have no impact on progression of the study. This interim analysis may occur when at least 50% of participants have been randomly assigned to study treatment and have completed the 26-week Initial Evaluation Period. This interim analysis, if performed, will be conducted by a separate unblinded team.

This interim analysis will include all planned efficacy, PK/PD, and safety analyses.

5.8.3. Early LN Interim Analysis

An early interim analysis may be conducted for the LN disease cohort when at least 50% of participants have been randomly assigned to study treatment and have completed the 26-week Initial Evaluation Period. This interim analysis, if performed, will be conducted by a separate unblinded team and will have no impact on the progression of the study.

This interim analysis will include all planned efficacy, PK/PD, and safety analyses.

5.8.4. Week 26 Analysis

A primary efficacy analysis will be performed for each disease-specific cohort at the end of the 26-week Initial Evaluation Period after all participants in the disease-specific cohort have completed or withdrawn from the 26-week Initial Evaluation Period.

This interim analysis will include all planned efficacy and safety analyses and available PK/PD.

5.8.5. Week 50 Analysis

An interim efficacy analysis will be performed for each disease-specific cohort at the end of the 50-week Extension Period after all participants in the disease-specific cohort have completed the Week 50 visit or withdrawn prior to the Week 50 visit.

This interim analysis will include all planned efficacy, PK/PD, and safety analyses.

6. SUPPORTING DOCUMENTATION

6.1. Appendix 1: Technical Specifications for Derived Variables

The following derived data will be calculated prior to analysis.

6.1.1. Disease Duration

Disease duration will be presented as the number of years between date of first infusion and date of diagnosis as reported on the medical history eCRF. Missing dates will be handled as in Section 5.1.4.

6.1.2. Definition of Baseline Values

For the Initial Evaluation Period, baseline is defined as the last available assessment value prior to the first dose of study intervention. For the Extension Period, baseline is defined as the last available assessment prior to the first dose of study intervention administered in the Extension Period.

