9.4.1. Efficacy Analyses

9.4.1.1. Analyses of Primary Efficacy Endpoint

The primary analysis of the primary efficacy endpoint will be based on the Full Analysis Set (FAS).

For the LN cohort, proteinuria will be measured by UPCR in g/g derived from a single 24-hour urine collection at Screening and the mean of 2 separate 24-hour urine collections at Week 26.

For the IgAN cohort, proteinuria will be measured by absolute protein in g/day derived from the mean of 2 valid 24-hour urine collections.

To reduce skewness, the natural logarithm will be used to transform proteinuria values before analysis. An analysis of covariance (ANCOVA) will be used for the primary efficacy endpoint to compare reductions in proteinuria between the ravulizumab and placebo treatment groups. The ANCOVA model will include change from baseline in log-transformed proteinuria as the response variable and will adjust for baseline log proteinuria and the randomization stratification factor. The treatment effect will be evaluated using the least squares mean difference between treatment groups. The point estimate and two-sided 90% confidence interval (CI) for the mean difference of log-transformed proteinuria will be back-transformed (via exponentiation) to obtain the GMR and corresponding two-sided 90% CI. The values will then be expressed as percentage change in adjusted geometric mean of proteinuria at Week 26 relative to baseline.

For the LN cohort, data collected on or after receipt of additional standard of care therapy will be imputed using the proteinuria value from the 24-hour urine collection performed at the time of Renal Flare for the primary efficacy analysis. Additional sensitivity analyses will be performed to assess the impact of the missing data and assumptions.

For the IgAN cohort, participants initially randomized to the placebo group will receive ravulizumab in the Extension Period. Therefore, analysis of the secondary endpoints during the Extension Period will be summarized separately for each treatment group and baseline for the placebo group will be re-defined as the last measurement taken before the first dose of ravulizumab during the Extension Period (ie, the Week 26 measurement).

The primary efficacy endpoint analysis will also be performed on the Per Protocol Set.

Full details of these analyses will be provided in the SAP.

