1.1. Objectives and Endpoints

Objectives	Endpoints
Primary (both cohorts)	
To evaluate the efficacy of ravulizumab compared with placebo to reduce proteinuria in adult participants with LN or IgAN	Percentage change in proteinuria from baseline to Week 26 (based on 24-hour urine collection[s] at each time point)
Secondary (both cohorts)	
To evaluate the efficacy of ravulizumab compared with placebo to improve measures of kidney function in adult participants with LN or IgAN	Percentage change in proteinuria from baseline to Week 50 (based on 24-hour urine collection[s] at each time point)
	Percentage of participants with > 30% and > 50% reduction in proteinuria at Week 26 and Week 50 compared to baseline (based on 24-hour urine collection[s] at each time point)
	Change from baseline in estimated glomerular filtration rate (eGFR) at Week 26 and Week 50
	Absolute values and change from baseline in serum C3 and C4 concentrations at Week 26 and Week 50

Objectives	Endpoints
Secondary (LN cohort only)	
To evaluate the efficacy of ravulizumab compared with placebo to improve measures of kidney function in adult participants with LN	Percentage of participants meeting the criteria for complete renal response (CRR) at Week 26 and Week 50
	Percentage of participants meeting the criteria for partial renal response (PRR) at Week 26 and Week 50
	Time to urine protein-to-creatinine ratio (UPCR) $\leq 0.5 \text{ g/g}$ as measured by spot urine sample
	Percentage of participants achieving corticosteroid taper to 7.5 mg/day at Weeks 14, 26, and 50
	Percentage of participants with renal flare through Week 50
	Percentage of participants with extrarenal systemic lupus erythematosus (SLE) flare through Week 50
	Percentage of participants with treatment failure through Week 50
	Percentage of participants with suboptimal response through Week 50
	Absolute values and change from baseline in serum albumin at Week 26 and Week 50
Secondary (IgAN cohort only)	
To evaluate the efficacy of ravulizumab compared with placebo on measures of kidney function in adult participants with IgAN	Percentage of participants meeting the criteria for partial remission at Week 26 and Week 50
Pharmacokinetic (PK)/pharmacodynamic (PD)/immunogenicity (both cohorts)	
To characterize the PK/PD of ravulizumab in adult participants with LN or IgAN	Absolute values and change from baseline in total C5 and free C5 concentrations over time

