During the 24-week Extension Period, participants in the LN cohort will continue to receive their randomized allocation of study intervention (ravulizumab or placebo) q8w. For the IgAN cohort, participants in the placebo treatment group will receive a blinded loading dose of ravulizumab at Week 26, and participants in the ravulizumab treatment group will receive a blinded ravulizumab dose of 900 mg at Week 26. Starting at Week 28, all participants in the IgAN cohort will receive open-label weight-based doses of ravulizumab q8w until the end of the Extension Period.

During the 36-week Post-treatment Follow-up Period, all participants will continue to receive standard of care and will be monitored for safety, clinical events of interest, and kidney function. Participants who discontinue study intervention early and agree to remain in the study should continue to attend their scheduled protocol visits until Week 50. During these visits, all assessments except for administration of study intervention should be performed according to the Schedule of Assessments. Participants who withdraw from the study will be followed for safety until 8 weeks after the last dose of study intervention. The end of study is defined as the last participant's last visit in the Post-treatment Follow-up Period.

In the LN cohort, participants will receive additional standard-of-care therapy in the event of a protocol-defined renal flare or severe extrarenal SLE flare. After Week 26, participants may also receive additional standard-of-care therapy for protocol-defined suboptimal response.

The primary objective of the study is to evaluate the efficacy of ravulizumab compared with placebo to reduce proteinuria in adult participants with LN or IgAN.

Figure 1: Study Design Schematic – LN Cohort

[figure not shown]

Note: Randomization will be stratified by whether corticosteroid induction treatment was initiated prior to Screening versus during the Screening Period. Allowed concomitant therapy consists of corticosteroids and mycophenolate mofetil. Weight-based dosing regimen (see [Protocol Section 1.1](#)) will be based on the last recorded study visit body weight.

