5.1.1. Data Presentation for the Initial Evaluation Period

Data summaries for the Initial Evaluation Period will be presented by randomized treatment group (ie, “Ravulizumab” and “Placebo”) and overall, if applicable. For the IgAN cohort, summaries will be presented by treatment sequence (ie, “Ravulizumab to Ravulizumab” and “Placebo to Ravulizumab”). Baseline is defined as the last value prior to the start of study intervention. All assessments for Week 26 will be performed prior to dosing. Dosing on Week 26 will be considered the start of the Extension Period.

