5.1.2. Data Presentation for the Extension Period

Data summaries for the Extension Period will be presented by randomized treatment group and overall, if applicable. For the IgAN cohort, summaries will be presented by treatment sequence (ie, “Ravulizumab to Ravulizumab” and “Placebo to Ravulizumab”). In addition, baseline for the IgAN cohort will be defined as the last value prior to their initial exposure to ravulizumab.

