Secondary (key continuous endpoints)	Ravulizumab or placebo	Full Analysis Set	Percentage change from baseline to Week 50 in proteinuria (both cohorts) Change from baseline in eGFR at Week 26 and Week 50 (both cohorts)	Data on or after receipt of additional standard-of-care therapy (LN cohort only) will be imputed using the value collected at the time of renal flare or severe extrarenal SLE flare (or suboptimal after Week 26, if applicable) Data on or after treatment discontinuation will be assumed missing and handled in the MMRM as MAR	Mean of the variable in each treatment group

Table 1: Estimands

Estimand	Treatment	Population	Variable	Handling of IE	Summary Measure
Secondary (key binary endpoints)	Ravulizumab or placebo	Full Analysis Set	
Percentage of participants with > 30% and > 50% reduction in proteinuria at Week 26 and Week 50 compared to baseline (both cohorts)
 
Percentage of participants meeting the criteria for CRR at Week 26 and Week 50 (LN cohort only)
 
Percentage of participants meeting the criteria for PRR at Week 26 and Week 50 (LN cohort only)
 
Percentage of participants meeting the criteria for Partial Remission at Week 26 and Week 50 (IgAN cohort only)
	
Participants who receive additional standard-of-care therapy (LN cohort only) or discontinue treatment are assigned as nonresponders
	Proportion of the variable in each treatment group

Abbreviations: CRR = complete renal response; eGFR = estimated glomerular filtration rate; IE = intercurrent events; LN = lupus nephritis; MAR = missing-at-random; MMRM = mixed effect model for repeated measures; PK = pharmacokinetics; PRR = partial renal response

The secondary estimands for all other secondary endpoints are similar to above except the intercurrent events will be ignored and all data occurring on or after the intercurrent event will be analyzed as observed.

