5.4. Secondary Endpoint Analysis

The secondary efficacy analyses will be based on the FAS. These analyses will be descriptive in nature, and no adjustment for multiplicity will be performed.

The analyses for participants in the LN cohort and participants in the IgAN cohort will be conducted and reported separately. Participants in each disease-specific cohort will be analyzed as randomized, regardless of actual treatment received.

Summary statistics will be computed and displayed by treatment group and by visit, where applicable. Descriptive statistics for continuous variables will minimally include the number of participants, mean, SD, minimum, median, and maximum. For categorical variables, frequencies and percentages will be presented.

For the IgAN cohort, participants initially randomized to the placebo treatment group will receive ravulizumab in the Extension Period. Therefore, analysis of the secondary endpoints during the Extension Period (Week 26 through Week 50) will be summarized separately for each treatment group assigned during the Initial Evaluation Period (Baseline through Week 26).

During the Extension Period, baseline for the placebo treatment group will be redefined as the last measurement taken before the first dose of ravulizumab during the Extension Period (ie, the Week 26 measurement).

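### SAP 6.1.2 moves the Extension Period baseline to Week 26 in every arm, which contradicts SAP 5.1.2 for the IgAN ravulizumab arm and does not fit the LN cohort

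*SAP*

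**What the plan says.** SAP 6.1.2, in the appendix of derived variables, gives one baseline rule per period. For the Extension Period, "baseline is defined as the last available assessment prior to the first dose of study intervention administered in the Extension Period". The sentence names no cohort and no arm.

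SAP 5.1.1 fixes the start of that period: "Dosing on Week 26 will be considered the start of the Extension Period". It also places all Week 26 assessments before that dose.

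SAP 5.1.2, on presenting Extension data, has a different rule: "baseline for the IgAN cohort will be defined as the last value prior to their initial exposure to ravulizumab".

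SAP 5.4, discussing the IgAN switch, says that "baseline for the placebo treatment group will be redefined as the last measurement taken before the first dose of ravulizumab during the Extension Period". Protocol 9.4.1.1 says the same for IgAN: "baseline for the placebo group will be re-defined as the last measurement taken before the first dose of ravulizumab during the Extension Period". Neither mentions a reset for participants already on ravulizumab.

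For LN there is no switch. SAP 1.2 says that in the Extension Period "participants in the LN cohort will continue to receive their randomized allocation of study intervention (ravulizumab or placebo) q8w".

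SAP 6.1.3 and 6.1.4 compute change and percent change from whatever baseline applies. SAP 5.1 asks for efficacy and safety summaries separately by period, and 5.4.1 repeats this for proteinuria.

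**The concern.** The derivation appendix and the data-presentation section give different baselines for the same IgAN ravulizumab participants, so their Week 50 change values depend on which section the programmer follows. The SAP has no rule saying which prevails. Its list of departures from the protocol (SAP 6.5) mentions only hematuria, so nothing suggests that extending the placebo-only reset to every arm was a deliberate decision.

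For LN, where participants stay on blinded randomised treatment, a Week 26 baseline would make the Extension tables show only what happened after Week 26. Those tables would sit beside a Week 50 model that measures change from before treatment. A reader comparing them could take a maintained effect for no effect.

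**Working it through.** The plan states no figure that depends on this rule, so there is none to reproduce. The check has two parts.

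**1. The rules, arm by arm**

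| Arm | SAP 6.1.2 with 5.1.1 | Other sections | Result |
|---|---|---|---|
| IgAN placebo | Week 26 | Week 26 (SAP 5.1.2, 5.4; Protocol 9.4.1.1) | agree |
| IgAN ravulizumab | Week 26 | pre-Day 1 (SAP 5.1.2); no reset in 5.4 or Protocol 9.4.1.1 | direct contradiction |
| LN ravulizumab | Week 26 | no stated Extension baseline | inconsistency by inference |
| LN placebo | Week 26 | no stated Extension baseline | inconsistency by inference |

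Week 26 here means the pre-dose Week 26 value when there is one. The rule takes the last available assessment, so a participant without it falls back to an earlier value.

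The LN inference rests on three things:
- Treatment does not change at Week 26 (SAP 1.2).
- The Week 50 MMRM carries one log-baseline covariate per participant across all visits (SAP 5.4.1 and the code in 6.4.2).
- Partial renal response is defined once, against a single baseline value, for use at either Week 26 or Week 50 (SAP 5.4.5 and 6.1.12).

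**2. Size, for illustration only**

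Inputs from SAP section 3: the assumed Week 26-to-baseline geometric mean ratio g is 0.55 for IgAN ravulizumab, 0.40 for LN ravulizumab and 0.60 for LN placebo. The documents give no Week 50-to-Week 26 ratio r. I assume 0.8, 1.0 and 1.2, and log-normal changes, so that the ratios can be read as medians.

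- Week 50 change from pre-Day 1 = 100 × (g × r − 1)
- Week 50 change from Week 26 = 100 × (r − 1)

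For IgAN ravulizumab at r = 1.0: 100 × (0.55 × 1.0 − 1) = −45%, against 100 × (1.0 − 1) = 0%.

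| Arm | Baseline | r = 0.8 | r = 1.0 | r = 1.2 |
|---|---|---|---|---|
| IgAN ravulizumab | pre-Day 1 | −56% | −45% | −34% |
| LN ravulizumab | pre-Day 1 | −68% | −60% | −52% |
| LN placebo | pre-Day 1 | −52% | −40% | −28% |
| Each of these | Week 26 | −20% | 0% | +20% |

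Only the IgAN row compares two rules that the SAP actually states. The LN rows compare 6.1.2 with the baseline that the LN design and model imply.

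**The case against.** The strongest reply is that the IgAN-specific statements (SAP 5.1.2 and 5.4, Protocol 9.4.1.1) are compatible with one another, and that 6.1.2 is a single general sentence in an appendix which a sensible programmer would not let override them. The table specifications are in a separate Data Presentation Plan, so an effect on any output is not established. This stands as a limit on severity. It does not remove the contradiction, because 6.1.2 is the section meant to define derived variables. Reading it as the first-ever dose of ravulizumab would reconcile it with 5.1.2, but the sentence refers to study intervention given in the Extension Period, and the IgAN ravulizumab arm is dosed at Week 26.

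A reader might infer more than the documents support, in three ways:

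- *That LN is directly contradicted too.* It is not. No section gives a pre-Day 1 Extension baseline for LN, and a Week 26 baseline is an available, if unusual, descriptive choice. Nor does the endpoint wording "Percentage of participants with > 30% and > 50% reduction in proteinuria at Week 26 and Week 50 compared to baseline" settle the matter: it leaves baseline undefined and also covers the IgAN placebo arm, which is reset.
- *That the proteinuria responder rates or LN partial renal response would collapse.* That requires 6.1.2 to be applied over those endpoints' own definitions, which no section says. Any figure would also need an assumed Week 26-to-50 variability that the documents do not give.
- *That the LN treatment effect at Week 50 would vanish.* The LN Week 50 ratio comes from the MMRM, which uses one baseline covariate and is not exposed.

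**Conclusion.** The concern holds within limits. SAP 6.1.2 contradicts 5.1.2 for the IgAN ravulizumab arm and goes beyond the placebo-only reset in SAP 5.4 and Protocol 9.4.1.1. For LN it is an inconsistency with the design, the Week 50 model and the partial renal response definition, not a clash between two stated rules.

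If 6.1.2 is followed, the affected outputs are the by-period descriptive change tables for the Extension Period: for example proteinuria and C3/C4 in the IgAN ravulizumab and LN arms, LN serum albumin, and safety laboratory values for IgAN ravulizumab. Not affected are the Week 26 primary analysis, the LN Week 50 MMRM contrast, eGFR in the non-switching arms (which has its own baseline in SAP 5.4.2), and endpoints set by an absolute threshold.

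The shift of 45 percentage points for IgAN ravulizumab rests on the planning ratio of 0.55 and an assumed flat course after Week 26. Over the assumed range of r, the gap between the two baselines is 36 points at r = 0.8 (−56% against −20%) and 54 points at r = 1.2 (−34% against +20%). Severity is minor to should-fix, since only descriptive secondary and safety outputs are exposed.

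**What to change.** Replace the second sentence of SAP 6.1.2 with text such as:

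> For the Extension Period, baseline is re-defined only for IgAN participants randomised to placebo: it is their last assessment before they first receive ravulizumab (the Week 26 measurement), for all endpoints including proteinuria and eGFR. IgAN participants randomised to ravulizumab keep the pre-Day 1 baseline (Section 5.1.2). LN participants keep the pre-Day 1 baseline for efficacy endpoints. For these non-switching participants, the endpoint-specific baselines in Sections 5.3.1 and 5.4.2 apply.

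The limit in the last sentence matters. If 5.3.1 and 5.4.2 took precedence in every arm, their screening-period and Day 1 baselines would cancel the IgAN placebo reset for proteinuria and eGFR.

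Add one sentence naming the LN baseline for Extension safety summaries, which only 6.1.2 now supplies. Then check the Data Presentation Plan against the corrected text before the Week 50 analysis.

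The cost is a few sentences and a specification check. No new data are needed.

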6.1.3. Change from Baseline

Change from baseline will be calculated as the baseline value subtracted from the value at a particular time point. If 1 of the values is missing and there are no prespecified missing value imputation rules (see Section 5.1.4), then a change from baseline will not be calculated.

6.1.4. Percent Change from Baseline

Percent change from baseline will be calculated as (Change from baseline/Baseline value) x 100. If 1 of the values is missing and there are no prespecified missing value imputation rules (see Section 5.1.4) or if the baseline value is zero, then a percent change from baseline will not be calculated.

6.1.5. Analysis Visits

Summaries over postbaseline time points or analyses at specific postbaseline time points will be performed based on the list of visits described in the schedule of assessment of the protocol. For all assessments, the number of days from baseline will be calculated using the following formula: (date of assessment) - (date of first study treatment) + 1. Relative days prior to Day 1 are calculated as (date of assessment – date of Day 1 visit). This number of days will be used to assign analysis visit.

The analysis visit assignment for a specific assessment will be based on visit windows around each scheduled visit for that specific assessment. The windows for each scheduled visit will go from the midpoint (in days) between the current visit and the previous scheduled visit to the midpoint between the current visit and the subsequent scheduled visit. If the interval separating 2 scheduled visits is an even number of days, that middle day will be included in the later visit window and excluded from the prior visit window. For example, for an assessment with a scheduled visit Day 127, and a prior scheduled visit Day of 113 and subsequent scheduled visit Day of 141, the window will start at 120 days from baseline and will go to 133 days from baseline.

